## A.2. Subjects

A.2.1. Total number of subjects proposed across all sites by all investigators (provide exact number; if unlimited, enter 9999):

90

A.2.2. Total number of subjects to be studied by the UNC-CH investigator(s) (provide exact number; if unlimited, enter 9999):

90

A.2.3. If the above numbers include multiple groups, cohorts, or ranges or are dependent on unknown factors, or need any explanation, describe here:

All patients will be adult patients undergoing primary total hip arthroplasty. Patients will be randomly and evenly divided into two groups. One receiving the NPWT treatment and the other receiving our standard post surgical dressing.

A.2.4. Do you have specific plans to enroll subjects from these vulnerable or select populations:

**Do not check if status in that group is purely coincidental and has no bearing on the research. For example, do not check 'UNC-CH Employees' for a cancer treatment study or survey of the general public that is not aimed at employees.**

Children (under the age of majority for their location)

Note that you will be asked to provide age ranges for children in the Consent Process section.

Non-English-speaking

Prisoners, others involuntarily detained or incarcerated (this includes parolees held in treatment centers as a condition of their parole)

Decisionally impaired

Pregnant women

HIV positive individuals

UNC-CH Students

Some research involving students may be eligible for waiver of parental permission (e.g., using departmental participant pools). [See SOP 32.9.1](#)

UNC-CH Employees

UNC-CH Student athletes, athletic teams, or coaches

People, including children, who are likely to be involved in abusive relationships, either as perpetrator or victim.

This would include studies that might uncover or expose child, elder or domestic abuse/neglect. ([See SOP Appendix H](#))

A.2.5. If any of the above populations are checked, describe how you plan to confirm status in one or more of those groups (e.g., pregnancy, psychological or HIV testing)

No Answer Provided

A.2.6. If any of the above populations are checked, please describe your plans to provide additional protections for these subjects

No Answer Provided

A.2.7. Age range of subjects:

Minimum age of subject enrolled	18
	years
Maximum age of subject enrolled	99
» If no maximum age limit, indicate 99	years

### A.3. Inclusion/exclusion criteria

A.3.1. List required characteristics of potential subjects (i.e., inclusion and exclusion criteria). If not covered, list also characteristics that would preclude their involvement.

#### Inclusion Criteria:

Adult patients undergoing primary total hip arthroplasty.

#### Exclusion Criteria:

- age less than 18 y/o

- Total hip arthroplasty for fracture

- Revision or conversion total hip arthroplasty

- inability to personally consent to participation due to cognitive impairment, intoxication or sedation

- multiple surgical procedures

- Patients taking immune modulating medication(prednisone, methotrexate, anakinra, etc...)

- skin hypersensitivity to acrylic adhesive or silver.

- Inability to care for dressing due to physical or mental incapacitation

A.3.2. Justify any exclusion based on race, gender or ethnicity

Individuals will have equal opportunity to participate in the study regardless of gender, race and ethnicity.

A.3.3. Will pregnant women or women who become pregnant be excluded?

No

### A.4. Study design, methods and procedures

*Your response to the next question will help determine what further questions you will be asked in the following sections.*

A.4.1. Will you be using any **methods or procedures commonly used in biomedical or clinical research** (this would include but not be limited to drawing blood, performing lab tests or biological monitoring, conducting physical exams, administering drugs, or conducting a clinical trial)?

Yes

A.4.2. Describe the study design. List and describe study procedures, including a sequential description of what subjects will be asked to do, when relevant.

Patients will undergo primary total hip arthroplasty with identical preoperative and intraoperative care. The patients will then be divided into two groups depending on their randomization. All postoperative care will remain the same other than the choice of dressing placed postoperatively. They will remain in the hospital for 2-3 days(standard of care). On Post op day two they will receive a dressing change regardless of their regimen(standard of care). Patients will be discharged home or to a skilled nursing facility with instructions regarding wound care in both regimens. They will receive assistance through home health or through their nursing facility in case of dressing issues although there will be no intended dressing change or other alteration of the dressing until their next followup. Instructions for the study will be included in the discharge instructions and

include a phone number for questions, these instructions are provided on another attachment. The patients will return to clinic on Post op day seven. They will have their wound evaluated and the dressing changed with their wound evaluated for ASEPSIS (the details of the scoring system and references are provided in the background). They will return on post op day 14 and again have their wound evaluated. Their staples will also be removed. They will be monitored until their 6 week visit for any complications.

Standard Regimen.

Post Op Dressing	Staples over surgical incision, Adaptic® dressing, Abdominal Dressing pad, Tape
POD2	All dressings removed, staples remain in place, Island dressing placed
1 Week Post Op	Island dressing removed and new sterile island dressing placed *Wound evaluated
2 Weeks Post Op	Island dressing removed and staples removed, no dressing placed *Wound evaluated

Experimental Regimen.

Post Op Dressing	Staples over surgical incision, NPWT dressing
POD2	Dressing removed, staples remain in place, New sterile NPWT dressing placed

	NPWT dressing removed and sterile island dressing placed
1 Week Post Op	*Wound evaluated
2 Weeks Post Op	Island dressing removed and staples removed, no dressing placed *Wound evaluated

The evaluations to be recorded, and the occasions of evaluation, are detailed in **Table 1a** and **Table 1b**.

**Table 1a. Measurements Recorded: Patient Profile Data**

Domain	Name of Variable	Description of the Variable	When Recorded
Identifiers	patient_ID	unique patient ID for this study	All occasions
	date	Date of each occasion	All occasions
	treatment_group	Treatment regimen assigned	Enrollment
Patient Factors	age	age in years	Enrollment
	gender	sex( male, female)	Enrollment
	allergies	list of allergies	Enrollment
	medical_history	medical history	Enrollment
	side	Side( left, right)	Enrollment
	co-morbidities	List of co-morbidities	Enrollment
Compliance	adherence	Self-reported adherence to protocol	All visits

**Table 1b. Measurements Recorded: Treatment and Response Data**

Measurement	1 Week Post op	2 Weeks Post op
Serous Exudate	X	X
Erythema	X	X
Purulent Exudate	X	X

Separation of Deep Tissue	X	X
Antibiotic Treatment	X	X
Local Debridement	X	X
Operative Debridement	X	X
Positive Bacterial Culture	X	X
Hospitalization >14 days	X	X
Adverse Events	X	X

A.4.3. If subjects are assigned or randomized to study "arms" or groups, describe how they are assigned.

- *Describe the methods of computing the randomization schedule (if any) and maintaining blinding (if any).*
- *Who will perform these computations?*
- *How will you verify each subject's eligibility prior to randomization?*

Treatment regimen will be assigned to research subjects by a randomization procedure performed through the REDCap software. An independent member of the TraCS team and software manager ([name]) will assist in developing the randomization. Prior to surgery the research team will be informed of the selected treatment group and provide the dressing to the surgeon intraoperatively. Subsequently, the assigned treatment may be adaptively modified in some ways to protect the well-being of the subject. Such modifications may create a departure from protocol.

Randomization procedure. The randomization procedure will assign the research subjects (i.e., the experimental units) to the two treatment regimens in a 1:1 ratio. De

Blinding. This will be an unblinded, open-label study. Both patients and their respective care teams will be aware of the treatment regimen to which each patient has been randomized at the time of enrollment, at the time of informed consent and throughout treatment.

Protocol Departures. Although early termination of the subject's dressing is not anticipated, it is possible that some research subjects will require modifications of their dressing or care that constitute departure from the assigned treatment regimen. A case by case decision will be made to either continue the protocol or to drop the patient from the study and make needed changes. Protocol departures will be carefully documented. Subjects whose medical care departs from the protocol will continue to be evaluated per protocol and the resulting data will be recorded in the database for use in intent-to-treat (ITT) statistical analyses.

A.4.4. Describe any follow up procedures.

Followup is standardized and in keeping with normal postoperative care. Evaluation of the wound will occur during followup, however no additional procedures will be required.

A.4.5. Once this study has been approved by the IRB, for how many months or years will this study be active (you are collecting data or have access to identifiers)?

Start:Following IRB approval

Stop: 1 year from start date or earlier depending on number enrolled

A.4.6. Will this study use any of the following methods?

- Audiotaping
- Videotaping or filming
- Behavioral observation - (e.g., Participant, naturalistic, experimental, and other observational methods typically used in social science research)
- Pencil and paper questionnaires or surveys
- Electronic questionnaires or surveys
- Telephone questionnaires or surveys
- Interview questionnaires or surveys
- Other questionnaires or surveys
- Focus groups
- Diaries or journals
- Photovoice
- Still photography

A.4.7. If there are procedures or methods that require specialized training, describe who (role/qualifications) will be involved and how they will be trained.

Physical examination will be performed by 2 orthopaedic clinic members that do not require additional training. Dressing care will be provided by nursing staff, home health, and skilled nursing facilities with proper training. The nurses involved in patient care are not required to do any additional tasks. They can monitor the status of the dressing and will inform the clinic team if a dressing is malfunctioning. They will not be asked to do dressing changes. The device is designed to not require any daily maintenance.

A.4.8. Are there cultural issues, concerns or implications for the methods to be used with this study population?

No

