## Part B. Direct Interaction

### B.1. Methods of recruiting

B.1.1. Check all the following means/methods of subject recruitment to be used:\*

- In person
- Participant pools
- Presentation to classes or other groups
- Letters
- Flyers
- Radio, TV recruitment ads
- Newspaper recruitment ads
- Website recruitment ads
- Telephone script
- Email or listserv announcements
- Follow up to initial contact (e.g., email, script, letter)
- Other

B.1.2. Describe how subjects will be identified

Patients will be patients previously scheduled for primary total hip arthroplasty in [name] clinic.

B.1.3. Describe how and where subjects will be recruited and address the likelihood that you will have access to the projected number of subjects identified in A.2.

All patients will be previously scheduled for primary total hip arthroplasty in [name] clinic. [name] performs approximately 10 primary total hip arthroplasties per month.

B.1.4. Describe how you will protect the privacy of potential subjects during recruitment

All patient data will remain on secured servers.

B.1.5. Describe how subjects will be contacted, if not addressed above

Subjects will be previously scheduled for clinic visits in preparation of total hip arthroplasty surgery.

B.1.6. Describe who will do the recruiting

Recruiting will be performed by the resident surgeon during clinic visits.

B.1.7. Describe efforts to ensure equal access to participation among women and minorities

All patients regardless of demographics will be recruited. No difference in recruiting efforts will be made.

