## D.1.2. Will adult subjects be enrolled in your study?

Yes

Explain the process for obtaining consent from the subject or the subject's legally authorized representative, if relevant

Patient's will be consented during their preoperative clinic visits. These visits have been previously scheduled for their surgery.

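### The arm is known before surgery although the dressing is needed only after stapling, which leaves the promised identical operative care open to avoidable performance bias and lets patients be randomised before eligibility is final

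*Combined protocol and SAP*

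**What the plan says.** - **Release of the arm (A.4.3).** "Prior to surgery the research team will be informed of the selected treatment group and provide the dressing to the surgeon intraoperatively".
- **Who knows it, and from when (A.4.3, Blinding).** "Both patients and their respective care teams will be aware of the treatment regimen". The paragraph dates this knowledge from enrollment and consent onward. Table 1a likewise records the treatment group at enrollment.
- **Consent (D.1.2).** "Patient's will be consented during their preoperative clinic visits".
- **Recruitment (B.1.6).** "Recruiting will be performed by the resident surgeon during clinic visits".
- **Design sequence (A.4.2).** "Patients will undergo primary total hip arthroplasty with identical preoperative and intraoperative care. The patients will then be divided into two groups depending on their" (cut here for length; the sentence goes on to name the random assignment). In both regimen tables the first entry is staples over the incision, followed by the dressing.
- **Eligibility (A.3.1, A.4.3).** The exclusions include immune-modulating medication, inability to care for the dressing, and "multiple surgical procedures", which is not defined. The form asks how eligibility is verified before randomisation. The text available to us gives no answer.
- **Departures (A.4.3, Protocol Departures).** "A case by case decision will be made to either continue the protocol or to drop the patient from the study and make needed changes". The same paragraph says that subjects whose care departs from protocol continue to be evaluated and that their data are used in the ITT analyses.
- **Primary test (A.8.1).** An unadjusted two-group t-test on the one-week ASEPSIS score, justified by randomisation balancing the groups on covariates.

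**The concern.** Randomisation balances only what precedes it. If the team knows the arm before the first incision, operative technique and intraoperative events come after allocation, and the reason given in A.8.1 for an unadjusted comparison no longer covers them. Haemostasis and closure plausibly affect serous exudate, erythema and tissue separation, and these items are scored for the primary endpoint at one week. A small difference in how carefully wounds are closed, conscious or not, would appear in the result as an effect of the dressing.

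There is also a gap between the clinic visit and the end of the operation. During it an operation can be cancelled, the surgical plan can change, or an excluded drug can be started. A patient already assigned at that point is either analysed without having received either dressing or removed after randomisation by people who know the arm. The plan does not say which.

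**Working it through.** **1. Sequence set side by side**

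| Step | Source | Arm known? |
|---|---|---|
| Recruitment and consent at preoperative clinic | B.1.6, D.1.2 | Yes, according to the Blinding paragraph |
| Research team told the arm | A.4.3 | Yes, before surgery |
| Operation, haemostasis, stapling | A.4.2 | Yes for care teams, according to the Blinding paragraph |
| Assigned dressing first needed | A.4.2 regimen tables | This is the first step that requires the arm |

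Everything between the second and the last row is done with the arm known, and no step in that interval needs it.

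**2. Could a difference in operative care be detected or adjusted for?** Table 1a lists identifiers, patient factors and self-reported adherence. It has no operative variable such as duration, blood loss or closure details. Beyond naming staples in both arms, A.4.2 does not standardise closure. A difference between arms could be neither seen nor adjusted for.

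**3. What happens to a patient randomised but then cancelled or ineligible?** The Protocol Departures paragraph concerns modifications of dressing or care after assignment, and its ITT sentence covers subjects whose care departs from protocol. Neither clearly covers a patient who was never operated on or who proved ineligible before a dressing was applied.

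**4. Size in terms of power.** The plan's own figure comes first. Inputs from A.8.4 are 40 per arm and a difference of 0.63 SD. Alpha is not stated, so two-sided 0.05 is assumed.

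- Normal approximation: power = Φ(0.63 × √(40/2) − 1.96) = Φ(2.817 − 1.960) = Φ(0.857) = 0.804. This reproduces the stated 80%.
- Exact noncentral t: 0.795, with a detectable difference of 0.634 SD at 80% power.
- Allowance for incomplete data: 90 − 80 = 10 subjects.

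The documents give no rate of cancellation or late ineligibility. As an illustration only, suppose a further fraction of the 80 completers is lost for this reason:

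| Assumed extra loss | n per arm | Power at 0.63 SD (exact t) |
|---|---|---|
| 0% | 40 | 79.5% |
| 2% | 40 × 0.98 = 39.2 | 78.6% |
| 5% | 40 × 0.95 = 38 | 77.3% |
| 10% | 40 × 0.90 = 36 | 75.1% |

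If such losses fell within the allowance of 10, power would not fall below the plan's figure at all. The size of any bias from closure cannot be calculated from the documents.

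**The case against.** The strongest reply is that the trial is declared open-label, so knowledge of the arm is neither hidden nor surprising. Recruitment appears to come from one surgeon's clinic, and both regimens specify staples, which narrows the room for arm-dependent technique. A.4.3 informs the research team. That the operating surgeon knows before closure follows only from the reference to care teams in the Blinding paragraph, and nothing says that the resident who recruits also closes the wound. Most exclusions can be settled before surgery. The randomisation paragraph also breaks off in the text available, so some procedural detail may be missing there.

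Much of this stands as a limit on strength. It does not remove the point, because a visible device makes unblinding unavoidable only after it is applied. Knowledge during the operation can be avoided.

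Three stronger readings are tempting, and the documents do not support them:

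- **That this is failed allocation concealment.** A surgeon who knows the arm while operating is unblinded, which is a risk of performance bias. The statement that the arm is known at informed consent raises a separate question about the order of consent and assignment.
- **That A.4.3 contradicts the promise of identical intraoperative care.** Knowing the arm does not make care differ. The A.4.2 wording on dividing patients into groups can mean carrying out an assignment already made. The promise is unprotected, not broken.
- **That the plan provides for dropping ineligible patients case by case.** That sentence concerns changes in dressing or care, and follow-up for ITT is stated in the same paragraph. For late ineligibility the plan has a gap, not a described practice.

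**Conclusion.** The concern holds as an avoidable weakness in design that should be corrected. The arm is available to the team throughout an operation that does not require it. No operative data are planned that could show whether care was in fact the same, and the primary test has no protection other than randomisation. The plan also leaves unstated what happens to a patient who is randomised and then cancelled or found ineligible.

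The main risk is bias in the one-week score. Its direction and size are unknown, and nothing in the documents shows that closure would differ between arms. The effect on power is small under the assumed losses: about 1 to 4 percentage points for 2% to 10% of completers, and none if the existing allowance absorbs them. The conclusion rests on two inferences: that care teams in the Blinding paragraph include those operating, and that eligibility or surgical plans can change between clinic and closure.

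**What to change.** In A.4.3, replace the sentence on informing the team before surgery with text to this effect: consent is obtained before surgery; after the incision is stapled, a team member re-checks the A.3.1 criteria in REDCap; only then is the allocation released and the assigned dressing opened. Add that patients who are cancelled or become ineligible before that point are recorded as not randomised, and that every patient randomised after it stays in the ITT analysis. The last clause concerns the analysis set only, not when a patient's care should change.

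Then bring three other places into line: the sequence in A.4.2, the time at which Table 1a records the treatment group, and the Blinding paragraph, which now places knowledge of the arm at enrollment and consent. A.2.1 and A.8.4 should say whether the 90 counts consented or randomised patients.

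The cost is protocol wording, one REDCap step, a minute or two at closure, and an unopened device kit on hand for each consented patient. The target of 40 per arm, the t-test and the dressing regimens do not change.

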#### **A.4.A. Biomedical methods and procedures**

A.4.A.1. Is this an interventional study that involves treatment, evaluation or diagnosis of a medical disease or condition?

Yes

If yes, distinguish what is being done specifically for this research from procedures that would be done anyway for clinical care:

The standard treatment is the placement of an absorptive dressing postoperatively after total hip arthroplasty. The patient receives a dressing change on Post op day 2. On POD7 there wound will be evaluated and dressing replaced and their staples removed on post op day 14.

The study group will have a negative pressure suction device place postoperatively (This will be the only difference). They will also receive a dressing change on postop day 2. On POD7 they will be

changed to an absorptive dressing and their staples removed on post op day 14.

The difference will be treatment for seven days postoperatively with a negative pressure suction device.

**A.4.A.2. Is this a Clinical Study?**

Check YES if this study involves research using human volunteers that is intended to add to medical knowledge. There are two main types of clinical studies: clinical trials and observational studies. Do NOT check yes merely because you are conducting research in a clinical setting or using clinical data.

[Click here for additional definition of "Clinical Study"](#) 

Yes

Will this clinical trial be listed in [ClinicalTrials.gov](#), either by you or the sponsor?

Yes

Choose the appropriate Phase designation for this clinical trial.

Pilot Study

Phase I

Phase I/II

Phase II

Phase III

Phase IV

Other

**A.4.A.3. If the study involves the use of placebo control, provide justification**

No Answer Provided

**A.4.A.4. Will this study involve drugs, biologics or other substances (such as a botanical or dietary supplement)?**

For guidance on dietary supplements, see Section VI, C [FDA guidance document UCM229175.pdf](#)

No

